after the last dose of IMP. Periodic abstinence, the rhythm method, and the withdrawal method are not acceptable methods of contraception. Male subjects should refrain from sperm donation throughout this period.

6. Body weight > 50.0 kg for men and > 45.0 kg for women and Body Mass Index within the range 18.5-30.0 kg/m^2 (inclusive).
7. Subjects must understand the nature of the study and must provide signed and dated written informed consent in accordance with local regulations before the conduct of any study-related procedures.
8. Subjects must be, in the opinion of the Investigator, able to participate in all scheduled evaluations, likely to complete all required tests, and likely to be compliant.
9. Subjects must be fluent in the local language.
10. Subjects must agree not to post any personal medical data related to the study or information related to the study on any website or social media site (e.g., Facebook, Twitter, etc.) until the trial has completed.

Individuals who meet any of the following **exclusion criteria** will not be eligible to participate:

1. A positive urine drug screen/alcohol test at Screening or Day -1.
2. Any history of psychiatric disorders, including substance use disorders, according to the Diagnostic and Statistical Manual of Mental Disorders, 5th Edition (DSM-5) criteria.
3. A diagnosis of intellectual disability (intellectual developmental disorder) or mental retardation.
4. Significant suicide risk as assessed by C-SSRS.
5. A positive Hepatitis B surface antigen or positive Hepatitis C antibody result at Screening.
6. A positive test for human immunodeficiency virus (HIV) antibody at Screening.
7. Alanine aminotransferase or aspartate aminotransferase levels greater than 1.5 times the upper limit of normal (ULN) at Screening or between Screening and first dose of tracer.
8. Frequently used any tobacco-containing (e.g., cigar, cigarette, or snuff) or nicotine-containing product (e.g., nicotine chewing gum, nicotine plasters, or other product used for smoking cessation) within 3 months prior to first dose of tracer. Frequent use is defined as 3 or more days per week. Use of any tobacco- or nicotine-containing product is prohibited within 1 week of first dose of tracer.
9. History of regular alcohol consumption within 12 months of the study defined as an average weekly intake of >21 alcoholic units/week for men or >14 alcoholic units/week for women.

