### **Trial Procedures and Assessments**

After assessing eligibility during a 3-week screening period, up to 10 healthy male subjects or female subjects will participate in the study. Subjects will be admitted to the study center on Day -1, the day before (first) tracer administration for baseline assessments and to (re-)confirm eligibility. Subjects will stay in the clinical unit for 5 days (4 nights) for imaging sessions 2 and 3. For the baseline PET scan, subjects may leave the unit in the evening. Blood samples for PK analysis will be collected pre-dose and at specified time points up to Day 4 post-dose (sessions 2 and 3). Physical examinations, vital signs, ECG, will be performed at specified times. Adverse events will be recorded throughout the study. A follow-up visit will take place 7 days ( $\pm$ 3 days) after receiving the last tracer dose. For details regarding the timing of specific procedures, see [Table 1](#).

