**Table 1: Visit and Assessment Schedule for Each Dose Level**

Day(s) (relative to PET scan)	Screening 		Imaging session 1 [Baseline PET] 		Imaging session 2 [on-treatment] 			Imaging session 3 [on-treatment] 			Follow-up visit or ET 
	Visit 1	Visit 2 [MRI]	Visit 3 (in-patient)		Visit 4 (in-patient)			Visit 5 (in-patient)			
			Day -1	Day 1	Day -1	Day 1	Day 4	Day -1	Day 1	Day 4	Day 8
Informed consent	X										
Inclusion/exclusion criteria	X		X		X						
Demographics	X										
Medical/surgical history	X										
Allen's test	X			X		X				X	
Admission			X		X				X		
Inpatient stay 											
MRI scan 		X									
Venous cannulation 				X		X			X		
Arterial cannulation				X		X			X		
Administration of [  F]-IMA601 				X		X			X		
PET scan 				X		X			X		
Dose of study drug 						X			X		
Discharge 				X				X		X	
Safety assessments											
Physical and neurol. examination 	X				X 			X 			X
Pregnancy and FSH 	X	X	X		X			X			X
Height, weight & BMI 	X	X									
Vital signs 	X		X			X			X		X
12-lead ECG 	X		X			X			X		X
Serology (including HBsAg, anti-HCV)	X										

Day(s) (relative to PET scan)	Screening 		Imaging session 1 [Baseline PET] 		Imaging session 2 [on-treatment] 			Imaging session 3 [on-treatment] 			Follow-up visit or ET 
	Visit 1	Visit 2 [MRI]	Visit 3 (in-patient)		Visit 4 (in-patient)			Visit 5 (in-patient)			
			Day -1	Day 1	Day -1	Day 1	Day 4	Day -1	Day 1	Day 4	Day 8
Hematology, biochemistry, coagulation, and urinalysis	X		X		X		X 	X		X 	X
Urine drug and cotinine screen and Alcohol Urine Test	X		X		X			X			
C-SSRS	X										X
Blood Samples											
PK plasma sampling 						X	X		X	X	
Arterial Blood Sampling				X		X			X		
Ongoing Subject Review											
Concomitant Medicines	←-----→								✗	✗	
Adverse Events	←-----→								✗	✗	

Abbreviations: C-SSRS = Columbia-Suicide Severity Rating Scale; ET = Early Termination; HBsAg = Hepatitis B surface antigen; HCV = Hepatitis C virus; MRI = Magnetic resonance imaging; PET = Positron emission tomography; PK = Pharmacokinetics; WOCBP = Women of childbearing potential.

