After each on-treatment PET scan, the SRC will review available RO, PK, safety and tolerability data, before selecting the dose and PET scan timings for imaging session 3. Arterial blood sampling will be done during each PET scan to quantify the parent tracer related radioactivity over the course of the PET scan, and to establish a tracer metabolite corrected plasma input function. The total arterial blood volume required for each tracer injection will not exceed 145 mL. Arterial cannulation and arterial blood sampling may be reduced or removed if analysis of PET data from previous subjects indicates that noninvasive analysis of the PET scan data can be done. If a non-invasive analysis is not possible, the use of an arterial cannula with each PET scan will continue through the study.

Subjects will be screened within 21 days before their baseline PET scan. Their on-treatment PET scans will be within 7 days of their baseline scan with an interval of 7–14 days between imaging sessions 2 and 3. Subjects will be confined for 72 h after the study drug administration in sessions 2 and 3. After the baseline scan in session 1 without study drug administration, subjects may leave the unit in the evening. In the case of a technical failure (such as unsuccessful tracer synthesis), subjects may be asked to attend an additional on-treatment imaging session, in which they will receive a third oral dose of ASN51. There will be at least 7 days between each dose of ASN51. Subjects will not have more than 3 PET scans or 3 doses of ASN51 during the study. Subjects will have a follow-up visit at the research unit 7 days ( $\pm$  3 days) after imaging session 3 (Day 8).

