### **7.2.2 Method of Assigning Subject Numbers to Treatment Groups**

Subjects will be sequentially assigned a screening identification number upon signing of informed consent. Once eligibility is confirmed (Day 1 of imaging session 1), subjects will receive a 4-digit number on Day 1 before the start of the day's study procedures. Subjects who replace discontinuing subjects who have started procedures/assessments on Day 1 will receive the number of this subject +1000, e.g., subject 2411 will replace subject 1411, subject 2211 will replace subject 1211, etc. The substitute subject will receive the treatment assigned to the withdrawn subject. The following subject numbers are assigned:

Subject numbers 1411 – 1420, replacement subject numbers 2411 – 2420

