**Exclusion Criteria:**

Individuals who meet any of the following **exclusion criteria** will not be eligible to participate.

1. A positive urine drug screen/alcohol test at Screening or Day -1.
2. Any history of psychiatric disorders, including substance use disorders, according to the Diagnostic and Statistical Manual of Mental Disorders, 5th Edition (DSM-5) criteria.
3. A diagnosis of intellectual disability (intellectual developmental disorder) or mental retardation.
4. Significant suicide risk as assessed by C-SSRS.
5. A positive Hepatitis B surface antigen or positive Hepatitis C antibody result at Screening.
6. A positive test for human immunodeficiency virus (HIV) antibody at Screening.
7. Alanine aminotransferase or aspartate aminotransferase levels greater than 1.5 times the upper limit of normal (ULN) at Screening or between Screening and first dose of tracer administration.
8. Frequently used any tobacco-containing (e.g., cigar, cigarette, or snuff) or nicotine-containing product (e.g., nicotine chewing gum, nicotine plasters, or other product used for smoking cessation) within 3 months prior to first dose of tracer. Frequent use is defined as 3 or more days per week. Use of any tobacco- or nicotine-containing product is prohibited within 1 week of first dose of tracer.
9. History of regular alcohol consumption within 12 months of the study defined as an average weekly intake of >21 alcoholic units/week for men or >14 alcoholic units/week for women.

10. Regularly consumed (e.g., more days than not) excessive quantities of xanthine-containing beverages (e.g., more than five cups of coffee or the equivalent per day) within 30 days prior to Screening or between Screening and first dose of tracer.
11. Received or used an investigational product (including placebo) or device within the following time period prior to the first tracer dosing day in the current study: 90 days, 5 half-lives or twice the duration of the biological effect of the investigational product (whichever is longer).
12. Other than exceptions outlined in [Section 9.10](#), use of prescription or non-prescription drugs, vitamins, herbal, and dietary supplements (including St John's Wort) within 7 days (or 28 days if the drug is a potential hepatic enzyme inducer) or 5 half-lives (whichever is longer) prior to the first dose of study tracer medication.

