13. History of clinically significant sensitivity to any of the study medications, or components thereof or a history of drug or other allergy that, in the opinion of the Investigator or Medical Monitor, contraindicates their participation.
14. Loss of more than 400 mL of blood within 3 months prior to first dose of tracer, i.e., blood donor.
15. A positive serum pregnancy test or lactation.
16. A history or presence of any disease, condition, or surgery likely to affect drug absorption, distribution, metabolism, or excretion. Subjects with a history of cholecystectomy should be excluded.
17. A history or presence of a clinically significant hepatic, renal, gastrointestinal, cardiovascular, endocrine, pulmonary, ophthalmologic, immunologic, hematologic, dermatologic, or neurologic abnormality.
18. A clinically significant abnormality on physical examination, neurological examination, ECG, or laboratory evaluations at screen or between screen and first tracer dose administration.
19. A corrected QT interval measurement corrected according to the Fridericia rule (QTcF)  $> 450$  msec for males,  $470$  msec for females during controlled rest at screen or between screen and first tracer dose administration, or family history of long QT syndrome.
20. Any clinically significant abnormalities in rhythm, conduction, or morphology of the resting ECG and any abnormalities in the 12-lead ECG that, in the judgement of the Investigator or Medical Monitor, may interfere with the interpretation of QTc interval changes, including abnormal ST-T-wave morphology or left ventricular hypertrophy.
21. PR (PQ) interval shortening  $< 120$  msec (PR  $< 120$  msec but  $> 110$  msec is acceptable if there is no evidence of ventricular pre-excitation).
22. PR (PQ) interval prolongation ( $> 220$  msec), intermittent second- (Wenckebach block while asleep or in deep rest is not exclusionary) or third-degree AV block.
23. Persistent or intermittent complete bundle branch block (BBB), incomplete bundle branch block (IBBB), or intraventricular conduction delay (IVCD) with QRS  $> 120$  msec.

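### The ALT/AST and QTcF entry limits close at the drug-free session 1 tracer dose, so the tests already scheduled before the first ASN51 dose have no fixed ALT/AST or QTcF entry limit

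*Protocol*

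**What the plan says.** **Entry limits.** Exclusion 7 in protocol 8.2 applies to ALT or AST "levels greater than 1.5 times the upper limit of normal (ULN) at Screening or between Screening and first dose of tracer administration". The synopsis has the same limit and closing point: "upper limit of normal (ULN) at Screening or between Screening and first dose of tracer". Exclusion 19 sets QTcF limits of 450 msec for men and 470 msec for women, measured "during controlled rest at screen or between screen and first tracer dose administration". Exclusion 18 (clinically significant findings) has the same window, ending "laboratory evaluations at screen or between screen and first tracer dose administration".

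**When eligibility is confirmed.** The synopsis narrative places admission on "the day before (first) tracer administration for baseline assessments and to (re-)confirm eligibility". Section 7.2.2 assigns subject numbers "Once eligibility is confirmed (Day 1 of imaging session 1"). Session 1 is the baseline scan and includes no ASN51; the first ASN51 dose is on Day 1 of session 2.

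**What is scheduled before that dose.** In Table 1 the row "Inclusion/exclusion criteria" is marked at screening, session 1 Day -1 and session 2 Day -1. Safety labs are also marked on session 2 Day -1, and footnote 17 places an ECG before dosing on session 2 Day 1.

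**Timing.** Section 7.1 states: "Their on-treatment PET scans will be within 7 days of their baseline scan". SAP section 5 repeats this. The Table 1 footnote on admissions instead puts session 2 admission within 7 days of the baseline scan, and 10.7.1 allows 28 days for the on-treatment scans.

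**The concern.** The ALT/AST and QTcF limits protect healthy volunteers from exposure to ASN51 when the liver or the QT interval already looks abnormal. As worded, they protect only up to the tracer. The plan collects fresh labs and a fresh ECG just before first exposure and marks an entry check in the same session, but the dated criteria give that check no ALT/AST or QTcF value to apply.

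Consistent handling is at stake. Two volunteers with the same new ALT, AST or QTcF value before the first dose could be treated differently. Section 8.2 allows no waivers and treats departures from the entry criteria as major deviations, and SAP 12.2 counts entry without meeting the criteria as major. Because the windows have closed, dosing such a subject would breach neither exclusion 7 nor the QTcF value in exclusion 19, so it need not be recorded as a deviation from them. Under SAP 11.2 these same session 2 results also become the safety baseline, being the latest values before study drug.

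**Working it through.** **1. Are the tests really planned before the first ASN51 dose?** Section 10.6 gives 7 draws each for hematology, chemistry and coagulation. The lab row of Table 1 is marked at screening, session 1 Day -1, session 2 Day -1, session 2 Day 4, session 3 Day -1, session 3 Day 4 and follow-up, which is 7 and agrees. The session 2 Day -1 draw is therefore part of the plan. ECGs before the first ASN51 dose number three: screening, session 1 Day -1 and session 2 Day 1 pre-dose. The third lies outside the QTcF window.

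**2. How long is the interval from first tracer dose to first ASN51 dose?**

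- Section 7.1 and SAP section 5: session 2 scan within 7 days of baseline, with the dose before the scan, so at most 7 days.
- Table 1 footnote: admission (Day -1) within 7 days and the dose the next day, so 7 + 1 = 8 days.
- Section 10.7.1: on-treatment scans within 28 days, sessions 2 and 3 separated by 7 to 14 days. The session 2 scan could then fall as late as 28 - 14 = 14 to 28 - 7 = 21 days after baseline.

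The three places disagree. Seven to 8 days is the reading under 7.1 and Table 1, but it is not a firm maximum.

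**3. Which numeric rules cover a new finding in that interval?**

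| Finding before first ASN51 dose | Entry limit in force? | Section 7.6.1 |
|---|---|---|
| ALT >1.5 to <3 x ULN | No, exclusion 7 has closed | No rule |
| ALT 3 to <5 x ULN, no symptoms or rash, and bilirubin and INR not raised | No | May continue only if monitored at least weekly |
| ALT 3 x ULN or more with raised bilirubin, INR >1.5, or symptoms | No | May be removed |
| ALT 5 x ULN or more | No | May be removed |
| AST, any level | No, exclusion 7 has closed | No rule |
| QTcF, any level | No, the exclusion 19 value has closed | No rule |

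For example, ALT of 2 x ULN on session 2 Day -1, or QTcF of 465 msec in a man on Day 1 pre-dose, would have excluded the subject before the tracer but meets no numeric rule before ASN51.

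**4. Which limits stay open?** Exclusions 21 to 23 set PR (<120 or >220 msec) and QRS (>120 msec) limits with no closing date, so they reach the session 2 ECG. The urine screen in exclusion 1 refers to Day -1 without restriction to session 1. Exclusion 15 (pregnancy) is undated, and 10.4.5 requires a negative serum test within 24 hours before the first dose of IMP. The protocol therefore already ties one entry test to ASN51 itself.

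**The case against.** The strongest reply is that the tracer is a sensible point at which to close entry. It is the first study administration and brings radiation and arterial sampling; many criteria in 8.2 share that anchor. After it, the plan moves to rules for enrolled subjects: 7.6.1 with its higher ALT thresholds, SRC review before each dose (7.5.1, 7.5.3), the right to remove anyone judged to be at risk, and the undated judgement criteria (inclusion 1; exclusions 17, 20 and 31). A site could apply the same thresholds at the session 2 check in Table 1. The values would not be hidden either: SAP 13.5 lists out-of-range labs, and SAP 13.6.2 lists QTcF above 450 msec.

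Much of this stands. It shows that protection remains and that the practical risk is limited. It does not supply a fixed ALT/AST or QTcF limit, and if Table 1 was meant to reapply these limits, the wording of the criteria does not let it.

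A reader might infer more, without support:

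- **That no fixed entry limit applies to the session 2 labs and ECG.** The PR, QRS, urine screen and pregnancy criteria remain in force.
- **That exclusion 18 is a lost numeric limit.** It rests on judgement, and exclusions 17 and 20 largely cover the same ground without a date.
- **That every ALT rule from 3 x ULN is purely discretionary.** Section 7.6.1 sets a weekly-monitoring condition for 3 to <5 x ULN.

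**Conclusion.** The point holds for ALT/AST and QTcF only. From the session 1 tracer dose to the first ASN51 dose, at most 7 days under 7.1 and 8 under Table 1 and possibly longer under 10.7.1, ALT above 1.5 and below 3 x ULN and AST or QTcF at any level meet no numeric rule. At 3 x ULN and above, ALT falls under the removal and monitoring rules of 7.6.1.

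This rests on reading the criteria as written. The documents give no rate of new ALT, AST or QTcF abnormalities over such an interval, so no frequency is claimed; labs and ECG are also checked on session 1 Day -1, which makes new findings less likely.

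A fixed limit is lost, together with the deviation record that goes with it; subjects are not left unprotected. Safety and consistent handling are affected, and the primary PET endpoint is not. This is a cheap improvement.

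**What to change.** 1. In 8.2 and the synopsis, end the windows of exclusions 7 and 19, and of 18 for consistency, at the first dose of ASN51. Keep the thresholds. A window running from screening to that dose still covers session 1.
2. State in 2.0, 7.2.2 and Table 1 that eligibility is reconfirmed before the first ASN51 dose, using the session 2 Day -1 labs and the Day 1 pre-dose ECG. Table 1 now marks the check on Day -1, before that ECG, so its mark or a footnote must extend to Day 1 pre-dose.
3. In 7.2.1 and 7.6.3, allow replacement of subjects lost after the baseline scan but before IMP. Both sections now cover only subjects who have received IMP, whereas the numbering in 7.2.2 already provides for subjects who have started Day 1 procedures.

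Exclusion 24 (vital signs) is secondary: the synopsis limits it to screening and 8.2 to the first tracer dose, and the two could be aligned in the same amendment.

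**Cost.** A wording amendment, with REC/MHRA approval under 13.1. No lab or ECG is added, assuming that the Day -1 results are back before dosing, which the documents do not state. An occasional subject is lost after one baseline scan, at up to 2.1 + 0.36 = 2.46 mSv and 145 mL of arterial blood, and a replacement needs a baseline scan of their own.

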### 8.3 Subject Withdrawal

Please see [Section 7.6.1](#).

## **9.0 STUDY DRUGS**

### **9.1 Investigational Drug**

Asceneuron SA will provide ASN51 for clinical trial use in the form of [REDACTED]. ASN51 is provided in an immediate release [REDACTED] supplied in [REDACTED] dosage strengths. Investigational Medicinal Product (IMP) will be administered under the supervision of the Investigator or designee under fasted conditions. Each dose incl. date, time, witness will be recorded.

### **9.2 Study Drug Preparation**

All study drugs will be prepared (i.e., packaged and labeled in individual doses) by a pharmacist, or his/her designee. All study drugs will be dispensed by the Investigator or a person under his/her supervision together with another witness.

### **9.3 Study Drug Packaging**

Asceneuron SA will be responsible for the supply of the following drugs:

- [REDACTED] containing [REDACTED] of ASN51

The study drug will be packed and dispatched in containers. A batch release certificate will be provided, stating that the batches have been manufactured according to GMP. Study drugs are provided as [REDACTED] and supplied to the study center as a bulk shipment. Under the supervision of the pharmacist, the study drug will be packed per subject for each dosing occasion, according to the dosing specifications of the SRC.

### **9.4 Study Drug Labeling**

The trial medication will be packaged and labelled by the [REDACTED] Pharmacy, in accordance with The Rules Governing Medicinal Products in the EU (European Union), Volume 4: Good Manufacturing Practice (GMP), and with [REDACTED]'s Manufacturing Authorisation for IMPs (MIA(IMP)). The IMP labels will include all the information required by Annex 13 to GMP

### **9.5 Study Drug Administration**

While in the study clinic, subjects are not allowed to consume any food and beverages not provided by the institution. Standardized meals will be provided. An extra amount of tap water will be given if it is required for the intake of the study drug, that will be recorded.

The study drug will be administered together with 240 ml of tap water in fasted state following a minimum 10 h fast (no food or drink except water) and will fast for a further 4 h after their dose. Other than the water required to take the study medicine, water is not allowed from 2 h before until 2 h after dosing. These restrictions also apply to the session 1 baseline PET scan such that all PET scans are carried out under the same conditions.

## **9.6 Concomitant Medications and Therapy**

Investigators may prescribe any concomitant medications or treatments deemed necessary to provide adequate supportive care. All concomitant medications taken during the trial will be recorded with indication, dose information, and dates of administration.

